15.1 Schedule of oversight procedures

15.2 DSMB meetings

In accordance with NIH policy, a Data Safety Monitoring Board (DSMB) will be constituted. The DSMB will consist of members of the advisory committee: [name], [name], and [name]. The DSMB will report Adverse Events (AEs) to the Mount Sinai Institutional Review Board, the funding I/C, the NIH Office of Biotechnology Activities (OBA), and the Food and Drug Administration (FDA) in accordance with Investigational New Drug (IND) regulations. The DSMB will meet prior to subject enrollment and data collection and will meet at 6 month intervals thereafter to review study progress and monitor patient safety. The responsibilities of the DSMB will include: 1) overseeing the study's progress, 2) approving alterations or amendments to the study protocol, 3) monitoring safety and reviewing serious adverse events (SAE), 4) overseeing data quality, 5) reviewing the interim analyses and recommending early trial cessation if indicated. The PI will be responsible for providing the DSMB with all necessary information.

As per IRB policies, all SAEs regardless of relationship to the research will be reported to the IRB within 24 hours and will be listed in the annual IRB application for continuation or termination of the research. All expected non-serious adverse events that occur at a greater frequency or severity than anticipated and all unexpected non-serious adverse events will be reported to the IRB within 15 working days and summarized annually to the IRB in the continuation or termination applications. Reports of adverse events will also be reviewed by the PI and the primary mentor at their weekly meeting. Questions and concerns will be discussed with the DSMB during scheduled meetings or in between meetings if a more serious concern arises.

15.3 FDA annual reports

The IND for this study is held by [name]. [name] is responsible for maintaining compliance with FDCA (21 U.S.C. §§ 301 et. Seq.) as well as implementing regulations [title 21 of the code of federal regulations (CFR)]. All reporting requirements described in the IND will be met.

16.0 Provisions for research related injury

The physicians on the research team and the DSMB will address any adverse events or refer the study participants for specialized treatment, if appropriate. Adverse events will be recorded in CRF 2 and deaths will be recorded on CRF 12. Published data suggest that inhaled mometasone at this dose will not cause serious adverse events in this population. If a study participant develops an adverse event, decisions will be made on a case-by-case basis to determine if the patient should be withdrawn from the study.

As discussed above, there are risks associated with participation in the proposed project. As detailed in HRP 503, risks associated with participation are minimal and all efforts will be made to avoid these risks. Staff will be trained to minimize risks associated with phlebotomy and other collection procedures. With regard to the risks associated with inhaled mometasone, the risks of adverse events are extremely low with the proposed dose of study medication. Participants will be followed very closely to assess for adverse events (see Data Safety and Monitoring Plan). For individuals who benefit from ICS, all efforts will be made to make ICS available via prescriptions from the participant's primary provider after conclusion of the study. Individuals randomized to placebo will be contacted after study data are analyzed to inform them if ICS are beneficial. The PI will also offer to contact primary providers for patients randomized to placebo if they would like to begin treatment with ICS.

If at any time, a subject expresses verbal or nonverbal unwillingness to participate, the subject will be withdrawn from the study.

17.0 Procedures for study withdrawal

Any participant experiencing serious adverse events will be considered for exclusion after adjudication by the DSMB.

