1.4.3 DSMB responsibilities

The DSMB will report Adverse Events (AEs) to the Mount Sinai Institutional Review Board, the funding I/C, the NIH Office of Biotechnology Activities (OBA), and the Food and Drug Administration (FDA) in accordance with Investigational New Drug (IND) regulations. The responsibilities of the DSMB will include: 1) overseeing the study's progress, 2) approving alterations or amendments to the study protocol, 3) monitoring safety and reviewing serious adverse events (SAE) which includes: death, intubation for acute chest syndrome, intensive care unit admission, or pulmonary infection, 4) overseeing data quality, 5) reviewing the interim analyses and recommending early trial cessation if indicated. The PI will be responsible for providing the DSMB with all necessary information.

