6.1 Telephone follow up (week 2)

6.2 Overview

A follow up telephone call will be conducted 2 weeks after the patient is enrolled in the study. The goal of this phone call is to identify adverse events, to assess medication adherence, and pregnancy surveillance in female patients. Patients who become pregnant during the study will be asked to stop taking the medication and they will be withdrawn from the study. The phone script and event questionnaire (to assess for adverse events) is contained in CRF 2 – Adverse Events Form.

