8.8 Financial Incentives/additional pain diaries

Once data collection is complete, the SRC will give the participant a second packet of pain diaries to complete over the subsequent 8 weeks. The SRC will also give the patient their financial incentives based on the number of diaries properly filled out as indicated by the schedule below (table 1).

Table 1
Timeline of financial incentives

	Visit 1 – Baseline Week 0	Visit 2 Week 8	Visit 3- end Week Obs	Observation† Week 20
Participants expected	56	50	45	45
Gift Card (\$30) -	X	X	X	X
Metro card (\$11) – travel costs	X	X	X	X
Gift card for completion of pain diaries	< 15 diaries – 0\$ 15-25 – 10\$ (50%) 26-50 – 20\$ (40%) 51-56 – 30\$ (10%)	< 15 diaries – 0\$ 15-25 – 30\$ (50%) 26-50 – 60\$ (40%) 51-56 – 90\$ (10%)	< 15 diaries – 0\$ 15-25 – 10\$ (50%) 26-50 – 20\$ (40%) 51-56 – 30\$ (10%)	< 15 diaries – 0\$ 15-25 – 10\$ (50%) 26-50 – 20\$ (40%) 51-56 – 30\$ (10%)

†Observational follow up period will continue for 4 weeks after study completion to measure adverse events, changes in pain and the proportion who choose to continue ICS.

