14.1 Data Analyses

14.2 Primary and Secondary Outcomes: The primary outcome for the study is feasibility. **Feasibility** will be determined by calculating the proportion of randomized patients who complete follow up and a minimum of 30 pain diaries (as was required in the PiSCES study)⁷³ with good adherence to the study medication vs. the number enrolled. Other findings relevant to feasibility will include retention rate (% who complete the study), points of attrition, recruitment rates (# approached vs. # enrolled) and adherence (via dosage counters - use of more than 70% of doses) as a function of recruitment site (clinic vs. ED).

14.3 Potential outcomes for a definitive multi-center trial. We will collect outcome data which will yield imprecise estimates of effect on patient-oriented vaso-occlusive, respiratory and safety outcomes. Vaso-occlusion will be measured in 5 ways 1) daily pain diaries (see exploration of potential definitive outcomes), 2) ED visits for pain; 3) hospital admissions (or observation unit stays) for pain 4) hospital admissions for ACS and 5) Health-related quality of life (change in ASCQ-Me score). While a primary clinical outcome was not specified, sample size calculation were based on detecting a difference in pain diary data (see data analysis). Respiratory outcomes will include self-reports of symptoms from the SAC survey. Safety outcomes include infections, adverse reactions, pain, avascular necrosis, stroke and intracranial hemorrhage. Data Collection and management for

aim 1: Data will be collected by the PI or RC in the manner described in 'subject identification and recruitment' above. All ED screening forms (CRF 1) will be kept in a file in a locked cabinet in the PI's office. Relevant laboratory data will be extracted from the medical record onto case report forms (see CRFs). Data will then be manually entered into database REDCap database.

Hardcopies will be maintained in a locked file cabinet in the PI's office. Identifiable data will be kept in either the REDCap database or on harcopy locked in a file cabinet in the PI's office. Hardcopy with identifiable data will never leave the PI's office. All data that is shared outside of the PI's office (i.e with statistician) will be stripped of identifiers and participants will be identified only by a unique ID number.

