14.7 Exploration of potential definitive outcomes: For the pain diary self-report measures of pain a linear mixed repeated measures model will be implemented with the SAS procedure MIXED to compare mometasone and placebo. The nesting variable will be participant ID number; main effects will be time, treatment group and interaction of time by treatment group. This will allow for variability in the number of diaries completed and variable effects of ICS over time (expected to increase with duration of treatment). For the measures of vaso-occlusion with poisson distributions (frequency of hospital visits for pain, ED visits for pain and hospital visits for acute chest syndrome), multivariable negative binomial regressions will be performed to estimate rate ratios based on treatment assignment. We expect self-report HRQL measures (change in ASCQ-Me score) to be approximately normally distributed. Pain diary data will be expressed in terms of several summary measures as described in the PiSCES project including number of days in 'crisis', number of pain days, number of days requiring opiate use and mean pain severity.⁷¹ Categorical summary measures will be compared with χ^2 statistic, continuous variables will be compared with t-tests or non-parametric tests as appropriate. Additionally, for potential patient-oriented outcomes, a series of Bayesian analyses will be performed. For normally distributed variables (i.e. ASCQ-Me pain domains) a posterior distribution will be estimated for the difference between treatment groups. This will be achieved by using a non-informative Gaussian distribution as the conjugate prior. Markov-chain monte carlo simulation will be used to obtain random samples from the posterior distributions of each treatment group such that the distribution of the difference between treatments can be estimated. The same procedure will be used for other patient-oriented outcomes. For poisson distributed outcomes (ED visits, hospital admissions) a gamma prior will be

used, for binomial outcomes we will use a beta prior. All Bayesian analyses will be performed in R. Bayesian analyses will also be used to estimate adverse events if any occur.

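### Adverse events, SAEs and pregnancy can take randomized participants out of the study, and no provision is stated for collecting their later outcomes

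*Combined protocol and SAP*

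**What the plan says.** Section 17.0, on study withdrawal, contains one rule: "Any participant experiencing serious adverse events will be considered for exclusion after adjudication by the DSMB". It does not say whether exclusion means from the drug, the visits or the analysis set, or who decides once the DSMB has adjudicated. For adverse events in general, 16.0 says that "decisions will be made on a case-by-case basis to determine if the patient should be withdrawn from the study". The pregnancy rule is firm and has two steps: "Patients who become pregnant during the study will be asked to stop taking the medication and they will be withdrawn from the study". It stands in 6.2, 7.2, 8.6.1, 9.2, 10.5 and 11.4.

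Section 1.4.3 lists as SAEs "death, intubation for acute chest syndrome, intensive care unit admission, or pulmonary infection". In section 14.3, "Safety outcomes include infections, adverse reactions, pain, avascular necrosis, stroke and intracranial hemorrhage", and one of the vaso-occlusive measures is "4) hospital admissions for ACS". For event counts, 14.7 says that "multivariable negative binomial regressions will be performed to estimate rate ratios based on treatment assignment"; it states no offset for time observed.

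On follow-up, the footnote to Table 1 (8.8) says: "Observational follow up period will continue for 4 weeks after study completion to measure adverse events". Sections 8.6.1 and 10.5 have CRF 5 and CRF 6 given once the unblinded coordinator confirms that the participant stays in the study. The November 2015 entry in the schedule of protocol changes extends follow-up to 16 weeks for non-adherent participants. Section 2.3 says that the analysis plan covers intention-to-treat analyses and the handling of missing data. Section 14 as supplied contains no missing-data rule.

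**The concern.** Under intention to treat, a participant who stops study drug is still observed and still analysed in the randomized arm. Sections 16.0, 17.0 and the pregnancy sentences do not make that separation. If withdrawal or exclusion means leaving the study, later ACS admissions, infections, ED visits, diaries and questionnaires are no longer collected. For events before week 8, the week-8 eNO and sVCAM samples go too.

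For adverse events and SAEs, the trigger can itself be an outcome. Participants who have had a pulmonary infection or severe ACS are likely to differ in prognosis from the rest. If an inhaled steroid changes the frequency of either event, in either direction, the loss will differ between arms. The safety and vaso-occlusive estimates that are meant to inform a definitive trial would then rest on a selected group. The week-20 visit exists to look for adverse events after the steroid is stopped (11.1). A participant withdrawn after an SAE could miss it.

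Pregnancy is different. It is under surveillance but is not a listed outcome, so its removal rule causes avoidable missing data and not outcome-triggered loss.

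**Working it through.** No figure in the plan is in dispute, so the main check compares the texts. The arithmetic shows scale only, and every event rate in it is an assumption.

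**1. Does withdrawal mean lost data?** The pregnancy sentence names stopping medication and withdrawal from the study as two separate steps. Research dosing ends at week 16 (10.1), so at week 20 (11.4) the second step can only mean leaving the study. CRF 5 and CRF 6 depend on the participant staying in. Continued follow-up is written for non-adherent participants only. Nothing supplied provides for follow-up after withdrawal for an SAE, another adverse event or pregnancy.

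**2. Do the triggers overlap the outcomes?**
- Pulmonary infection (SAE) falls within infections (safety outcome).
- Intubation for ACS (SAE) is the severe end of ACS admissions (vaso-occlusive outcome).
- Pain diaries, ED visits for pain and pain admissions have no counterpart on the SAE list.
- Death ends follow-up under any rule.
- Any adverse event can trigger 16.0, which is wider but equally discretionary.

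**3. How many participants?** Section 3.0 gives 45 participants at 2:1, that is 30 and 15. Assumed SAE risk: 5 to 20%.
- 45 × 0.05 = 2.25 and 45 × 0.20 = 9, so about 2 to 9 come under the rule.
- One placebo participant is 1/15 = 6.7% of that arm; one mometasone participant is 1/30 = 3.3%.

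**4. What could this do to an event count?** Suppose events follow a Poisson process with mean m per participant, and follow-up stops at each event with probability q. The expected number counted is (1 − e^(−qm))/q.
- With q = 1, the share still counted is (1 − e^(−m))/m: 88% at m = 0.25, 79% at 0.5, 63% at 1 and 43% at 2.
- With a true rate ratio of 0.5, control mean m and no offset, the crude ratio is (1 − e^(−0.5qm))/(1 − e^(−qm)). For q from 0.5 to 1 it is 0.52 to 0.53 at m = 0.25, and 0.62 to 0.73 at m = 2.

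Here every counted event can trigger removal, so this is an outer case for outcomes that only partly overlap the SAE list. In this constant-rate model an offset for time observed would remove the drift. It would not do so if the withdrawal decision also reflects the expected course, or if the effect grows with time, as 14.7 expects for the diaries.

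**5. What could this do to the eNO comparison?** Section 14.11 states 80% power for 5 ppb and 90% for 5.8 ppb but gives no SD, so these figures cannot be reproduced from the plan's own inputs. At two-sided 5% with 15 against 30, 80% power implies a change-score SD of 5 / [(1.960 + 0.842) × √(1/15 + 1/30)] = 5.64 ppb. That SD gives 90.2% at 5.8 ppb, so the two statements agree with each other. If 5%, 10% or 20% of both arms were removed before week 8, power at 5 ppb would be 78%, 76% or 71%. This is an upper bound on the loss at those risks, because it assumes that every SAE occurs before week 8 and leads to removal.

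**The case against.** The strongest reply is that the SAE and adverse-event rules are discretionary: a participant is considered after adjudication, case by case. Exclusion might mean only from the drug. That stands, so loss of follow-up is possible and not certain. The pregnancy rule is not discretionary.

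The triggering event is not lost. Adverse events go on CRF 2 and deaths on CRF 12 (16.0), and SAEs are reported to the IRB within 24 hours (15.2). An SAE after week 8 cannot affect the week-8 biomarkers. Both points stand: only later data are at risk.

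The condition attached to CRF 5 and CRF 6 may have been written with the adherence check in mind, and 11.4 states no such condition for CRF 7. That is fair, but as written the condition covers anyone who is no longer in the study.

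The manual also refers to a protocol (5.2.1) and to a Data Safety and Monitoring Plan and HRP 503 (16.0). Follow-up after withdrawal may be settled there. This limits certainty but does not reconcile the sections supplied.

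A reader might infer two stronger points that the documents do not support.
- **Inflated feasibility.** If 30 of 45 succeeded (assumed) and nine excluded participants left the denominator, 30/45 = 66.7% would become 30/36 = 83.3%. But 3.0 and 14.2 set the denominator as the number enrolled, so an excluded participant counts as a failure and the result stays at 66.7%.
- **A board that sees results by arm chooses who is removed.** Section 17.0 gives the DSMB adjudication and does not say who decides. Sections 1.4.3 and 2.3 have the board review interim analyses and efficacy data, but no section says whether it sees them by arm.

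**Conclusion.** The concern holds in a limited form. As written, adverse events, SAEs and pregnancy can remove a randomized participant from the study, and nothing supplied keeps that participant's later outcomes in view. For SAEs the loss would depend on an outcome, chiefly pulmonary infection and severe ACS, and could differ by arm. That is contrary to the intention-to-treat analyses promised in 2.3. For pregnancy it is avoidable missing data without that link. The harm falls on the safety, vaso-occlusive and, for early events, biomarker comparisons, not on the feasibility proportion.

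About 2 to 9 of 45 participants would come under the SAE rule if 5 to 20% have an SAE. The number actually removed depends on decisions that the documents do not specify. The drift in the rate ratio and the loss of power shown above are illustrations under stated assumptions, not estimates for this trial. The direction of any bias between arms cannot be settled from the documents. The change is worth making because it is cheap and each participant is a visible share of a small arm.

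**What to change.** In 16.0, 17.0 and the six pregnancy sentences, separate stopping study medication from leaving follow-up, and leave the existing clinical rules on medication, including the pregnancy instruction, as they are. Suggested addition:

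> Stopping study medication follows the clinical rules already stated and does not by itself end participation. Unless consent is withdrawn, a participant affected by an adverse event, an SAE or pregnancy remains in scheduled outcome and safety data collection to week 20: telephone calls, questionnaires, pain diaries and counts of ED visits, admissions and infections. Other study procedures continue only where the investigator finds them clinically acceptable. The participant stays in the feasibility denominator and in all intention-to-treat and safety analyses, in the randomized arm. Exclusion does not mean removal from an analysis set.

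Amend 8.6.1 and 10.5 so that CRF 5 and CRF 6 are also given to these participants. In section 14, state how time observed enters the event-rate models and how missing data are handled.

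The cost is a protocol amendment and a few follow-up contacts with participants who are off drug. The calls, visits and forms are already scheduled. Data collected off drug may dilute an on-treatment effect; the per-protocol analysis mentioned in the schedule of protocol changes can address that question separately.

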18.1 Appendices

18.1

Appendix 3 – HIMC SOPs

Supplement 2: Screening and eligibility form

(Affix Label Here) Participant ID: _____	Date Form Filled Out: _____ day month year	IMPROVE Inhaled Mometasone to Promote Reduction of Vaso-occlusive Events
--	--	--

Screening questionnaire to determine eligibility

Group 1

1. Does the participant's chest ever sound wheezy or whistling occasionally even without having a cold?
 Yes No
2. Has the participant ever had an attack of wheezing that has caused him/her to be short of breath?
 Yes No
3. Does this participant ever get attacks of wheezing after he/she has been playing hard or exercising?
 Yes No

Group 2

4. Has a doctor ever said the (BIOLOGICAL) mother of the participant had asthma?
 Yes No
5. Has a doctor ever said the (BIOLOGICAL) father of the participant had asthma?
 Yes No

Group 3

6. Has a doctor ever said that the participant has asthma?
 Yes No
7. Does the participant still have asthma?
 Yes No
8. Does the participant take any asthma medications?
 Yes No

Group 4

9. During the past 2 months, how often did the participant awaken from sleep because of cough or wheeze?
 Never
 Almost every night
 At least once a week but not nightly
 At least once a month but not weekly
 At least once but not monthly
10. During the past 2 months, how often did the participant cough or wheeze during or after exercise?
 Never
 Almost every night
 At least once a week but not nightly
 At least once a month but not weekly
 At least once but not monthly
11. During the past 2 months, how often did the participant cough or wheeze during the day unrelated to exercise?
 Never
 Almost every night
 At least once a week but not nightly
 At least once a month but not weekly
 At least once but not monthly

GROUP 5

12. Is the patient currently experiencing a sickle cell pain crisis?
 Yes
 No
13. Over the past 12 months how many ED or hospital visits did you have for sickle cell pain?
 0-5
 6-10
 11-15
 >15 (EXCLUDE)
14. Have you been admitted or discharged from the hospital in the past 7 days?
 Yes
 No
15. FEMALE PATIENTS ONLY: Is the patient Pregnant?
 Yes
 No

Inclusion/Exclusion Scheme:

Participants are eligible if they do not answer 'never' to all questions in group 4

Exclude Participants if

- a. They answer yes to all 3 questions in group 1
- b. They answer yes to 2 questions in group 1 and 1 or more questions in group 2
- c. They answer yes to questions 6 and 7 or questions 6 and 8
- d. They answer yes to questions 12 , 14, 15 and >15 for question 13 in group 5

Investigator Approval of Eligibility: _____ Date: _____

Supplement 3: Inhaler training and adherence modules

(Affix Label Here)
 
Participant ID: _
	
Date Form Filled Out:
 
-----
 
day month year
	
Inhaled Mometasone to Promote Reduction of Vaso-occlusive Events

---	---	---

Protocol Orientation Module A

If you lose your medication

Contact study staff immediately:

[REDACTED]
[REDACTED]
[REDACTED]
[REDACTED]
[REDACTED]

Pain diaries

Pain diaries are included in your package. Try to fill out a pain diary every day. If you miss a day that's ok. You must fill out at least 30 diaries to stay in the study.

Your medicine

This package contains your medicine for this study. Take one puff of the medicine every day. The research coordinator will teach you how to use the inhaler.

(Affix Label Here) Participant ID: _____	Date Form Filled Out: - - - - - day month year	Inhaled Mometasone to Promote Reduction of Vaso-occlusive Events
--	--	--

**Protocol Orientation Module: Adapted from “BREATHE EASIER: AN
ADULT ASTHMA EDUCATION PROGRAM” and Mometasone
Package Insert**

“Breathe Easier”

Developed by the American Institutes for Research and
the Kaiser-Permanente Medical Group

National Heart, Lung, and Blood Institute

National Institutes of Health

National Asthma Education and Prevention Program

FOR ORAL INHALATION ONLY

Please read this leaflet carefully before taking this medication

This leaflet does not contain the complete information about this medication. If you have any questions about mometasone inhalation ask your health care provider or pharmacist.

IMPORTANT POINTS TO REMEMBER

- Use this medication regularly and at the same time each day, as prescribed by your health care provider. You or your child may not get the most benefit for 1 to 2 weeks or longer after starting the medication. If you or your child's symptoms do not improve in that time frame or if your condition gets worse, contact your health care provider.
- The cap is needed to use the TWISTHALER. Do not twist the mouthpiece with your hand. When the cap is removed from the TWISTHALER, the dose counter will count down by one, and show the number of doses available after this use.
- The inhaler delivers your medicine as a very fine powder that **you or your child may not taste, smell, or feel**. Do not take or give extra doses unless your health care provider has told you to.
- It is important to replace the cap after each inhalation to protect the inhaler from moisture.
- Do not use the inhaler if you notice that it is not working correctly. Take it to your health care provider or pharmacist.

UNDERSTANDING YOUR MEDICATIONS

MATERIALS FOR SESSION:

- twisthalers

As part of this study you will be given an inhaler. This inhaler may contain placebo (no medication) or it may contain a medicine called mometasone. Mometasone is part of a class of medications called corticosteroids.

This is a medication taken regularly every day even when you don't have any symptoms

Although they have a similar name, these steroids are very different from the anabolic steroids that have been in the news in recent years because of their ill-advised use by athletes to increase muscle mass.

Corticosteroids are:

- Anti-inflammatory-Corticosteroids are a very effective anti-inflammatory medication and help reduce or prevent edema and excess mucus in the bronchial tubes.
- Have delayed action-· Corticosteroids do not relax the muscles around the bronchial tubes and will not open the airways immediately as do the bronchodilators. For this reason, they may not *seem* to have any effects. However, over time they can be very beneficial in reducing inflammation.

Inhaled corticosteroids have very few side effects, when used in moderate doses, but they must be taken regularly to be effective.

Possible side effects: an unpleasant taste and gastrointestinal symptoms (e.g., nausea). They may cause a yeast infection ("thrush") in the mouth or bother the upper airways and cause coughing.

Proper Inhaler Use (10 minutes)

The medication that we have been discussing is administered by aerosol inhaler, and proper inhaler use is very important for maximum benefit. If inhalers are not used correctly, the medications don't help much because they can't get all the way down into the narrow airways. Many times patients stop using their inhalers (or, on the other hand, overuse their inhalers) because they think the medicine is not working. In reality, it's not working only because they aren't using it right.

Go over steps while you demonstrate correct usage.

Instruct participants to take one puff per day

Let's take a few minutes to review inhaler use and make sure each of you is using the best technique.

How To Use YOUR INHALER

HOW TO USE ASMANEX TWISTHALER OR GIVE TO YOUR CHILD

- Remove the ASMANEX TWISTHALER from its foil pouch and write the date on the cap label.
- Throw away the inhaler 45 days after this date or when the dose counter reads “00”, indicating the final dose has been inhaled, whichever comes first.
- Follow steps 1 and 2 below each time you inhale a dose from your ASMANEX TWISTHALER.

Inhaler Parts:

[figure not shown]
See Figures 1 and 2 below to become familiar with the inhaler parts.

Step 1: Open inhaler

Hold the inhaler straight up (upright position) with the colored portion (the base) on the bottom (see Figure 3 below). It is important that you remove the cap of the TWISTHALER while it is in this upright position to make sure that you get the right amount of medicine with each dose.

Holding the colored base, twist the cap in a counterclockwise direction to remove it (see Figure 3 below). As you lift off the cap, the dose counter on the base will count down by one. Removing the cap loads the TWISTHALER with the medicine that you are now ready to inhale.

IT IS IMPORTANT TO NOTE that the indented arrow (located on the white portion of the TWISTHALER, directly above the colored base) is pointing to the dose counter (see Figure 2).

Step 2: Inhale dose

Breathe out fully. Then bring the TWISTHALER up to your mouth or your child's mouth with the mouthpiece facing toward you or your child. Place the mouthpiece in your mouth or your child's mouth, holding it in a horizontal (on its side) position as shown below (see *Figure 4*). Firmly close your lips around the mouthpiece and take in a fast, deep breath. Since the medicine is a very fine powder, you may not be able to taste, smell, or feel it after inhalation. Do not cover the ventilation holes while inhaling the dose.

[figure not shown]

Figure 4: Inhalation

Remove the TWISTHALER from your mouth and hold your breath for about 10 seconds, or as long as you comfortably can.

IMPORTANT: DO NOT BREATHE OUT (EXHALE) INTO THE INHALER.

After you take your medicine, it is important that you wipe the mouthpiece dry, if needed, and then **REPLACE THE CAP**, firmly closing the TWISTHALER right away (see *Figures 5 and 6* below).

Be sure that the indented arrow is in line with the dose counter. Put the cap back onto the inhaler and turn it in a clockwise direction, as you gently press down. You'll hear a "click" to let you know that the cap is fully closed. This is the only way to be sure that your next dose is loaded the right way.

[figure not shown]

Figure 5: Closing the Inhaler

You'll hear a "click" to let you know that the cap is fully closed.

This is the only way to be sure that your next dose is properly loaded.

Figure 6: Closed Inhaler

IT IS IMPORTANT TO REPEAT STEPS 1 AND 2 EACH TIME YOU INHALE.

Rinse your mouth after using.

STORING YOUR INHALER

- Keep your inhaler clean and dry at all times. If the mouthpiece needs cleaning, gently wipe the mouthpiece with a dry cloth or tissue as needed. Do not wash the inhaler. Avoid contact with any liquids.
- **Store in a dry place at 25°C (77°F) [may range between 15-30°C (59-86°F)].**
- Keep your inhaler out of the reach of children.

HOW TO KNOW WHEN YOUR INHALER IS EMPTY

The inhaler has a dose counter on the colored base, which shows the number of doses left to use. As you lift off the cap to take your dose, the dose counter on the base will count down by one (if you began with the dose counter reading "30" this will cause the dose counter to now read "29"). Read the numbers from top to bottom.

When the unit reads "01" this indicates the last remaining dose. After dose "01" the counter will read "00". When you replace the cap, the unit will lock and then must be thrown away. Start using a new ASMANEX TWISTHALER as instructed by your health care provider.

Practical Solutions to Problems Using an Inhaler (10 minutes)

Sticking to a schedule for using an inhaler can be pretty demanding, especially if you take other medications or take them several times a day. If your schedule for medications is very complicated, you may want to discuss with your physician and see if a simpler schedule can be worked out. Sometimes people do all right during the week but have problems keeping on schedule on the weekend or on vacation or traveling because they're not following their regular routine. Handout 14 describes some practical solutions to problems like forgetting your medication, coping with unpleasant side effects, or being embarrassed when you have to use your inhaler in a public place. Let's take a minute to read over the handout and then talk about which of these solutions seems personally useful to each of you. You might also have some suggestions that aren't on the handout.

Practical Solutions to Problems Using an Inhaler

With particular reference to finding specific solutions for class members. Elicit participants' feelings about taking medications on a routine basis.

Overuse of Medications (10 minutes)

Medication *underuse* includes things like:

- Skipping doses
- Being careless about the timing of your doses
- Discontinuing routine medications altogether

The opposite side of the coin is medication *overuse*. Surprisingly, the two problems can often go together. When you skip your medications you may be tempted to double up to bring things back under control. *This is much harder on your body* and may even lead to dangerous drug reactions.

In general, there are two dangers associated with medication overuse:

- Overused medication can cause *more side effects* sometimes even severe toxic reactions.

PRACTICAL SOLUTIONS TO PROBLEMS USING AN INHALER

There are several common problems people have trying to stick to their medication plans. Here are some tips and hints for overcoming them.

Problems Solutions

1. Use alarm clocks or watches with built-in alarm functions
2. Take your inhaler at the same time as another regular habit, such as before or after you eat, before you brush your medication teeth, or when you go to bed. Keep them visible.
3. Carry your medicines with you at all times, in your purse, briefcase, etc.; pack in carry-on luggage when traveling.
4. Use a written medication schedule or keep a diary for several weeks until you begin to establish good medication taking habits.
5. Check before a trip to make sure you have enough medication to last until you come back home.

(Affix Label Here)
 
Participant ID: _
	
Date Form Filled Out:
 
-----
 
day month year
	
Inhaled Mometasone to Promote Reduction of Vaso-occlusive Events

---	---	---

Protocol Orientation Module B

If you lose your medication

Contact study staff immediately:

[REDACTED]
[REDACTED]
[REDACTED]
[REDACTED]
[REDACTED]

Pain diaries

Pain diaries are included in your package. Try to fill out a pain diary every day. If you miss a day that's ok. You must fill out at least 30 diaries to stay in the study.

Your medicine

This package contains your medicine for this study. Take one puff of the medicine every day. The research coordinator will teach you how to use the inhaler.

(Affix Label Here) Participant ID: _____	Date Form Filled Out: - - - - - day month year	Inhaled Mometasone to Promote Reduction of Vaso-occlusive Events
--	--	--

**Protocol Orientation Module: Adapted from “BREATHE EASIER: AN
ADULT ASTHMA EDUCATION PROGRAM” and Mometasone
Package Insert**

“Breathe Easier”

Developed by the American Institutes for Research and
the Kaiser-Permanente Medical Group

National Heart, Lung, and Blood Institute

National Institutes of Health

National Asthma Education and Prevention Program

(mometasone furoate inhalation)

FOR ORAL INHALATION ONLY

Please read this leaflet carefully before taking your medication.

This leaflet does not contain the complete information about this medication. If you have any questions about this medicine, ask your health care provider or pharmacist.

IMPORTANT POINTS TO REMEMBER

- Use your inhaler regularly and at the same time each day, as prescribed by your health care provider. You or your child may not get the most benefit for 1 to 2 weeks or longer after starting the medication. If you or your child's symptoms do not improve in that time frame or if your condition gets worse, contact your health care provider.
- The inhaler delivers medicine that **you or your child may not taste, smell, or feel**. Do not take or give extra doses unless your health care provider has told you to.
- It is important to replace the cap after each inhalation to protect the inhaler from moisture.
- Do not use the inhaler if you notice that it is not working correctly. Take it to your health care provider or pharmacist.

UNDERSTANDING YOUR MEDICATIONS

MATERIALS FOR SESSION:

- MHWUHG GRVH LQKDOHUV

